1 SYNOPSIS

Title:	Epidemiology of Priapism
CSCC Protocol Date:	February 10, 2006 Version 6.3
Overview:	Priapism, a prolonged erection of the penis that may lead to impotence, is a specific type of painful crisis that commonly occurs in patients with sickle cell disease. The current treatment of priapism can be improved by comparing therapeutic strategies in prospective clinical trials, but first an assessment of the natural history of priapism is needed. This project will conduct an interview of 1,650 males with sickle cell disease in order to determine in which patients, how often, and under what circumstances priapism occurs.
CSCC Protocol Chair:	[name].
Intervention:	Survey
Objectives:	
 1. Enumerate the cross-sectional prevalence, demographics, and common clinical characteristics of priapism in males with sickle cell disease among the CSCC patient population. 2. Identify patients eligible for randomized clinical trials of promising secondary prevention strategies. 
This will be accomplished by completion of the following specific aim(s):
 
 1. To conduct a questionnaire survey of 1,400 males with sickle cell anemia and sickle beta zero thalassemia 5 years of age or older in order to determine the prevalence (frequency) and characteristics (number and pattern of episodes, cause or precipitating event, treatment, and outcome) of priapism. 2. To survey 250 additional males with other forms of sickle cell disease with the same instrument and describe the occurrence and characteristics of priapism experienced. 3. To develop a structured educational brochure about priapism for patients with sickle cell disease. 4. To identify the number of patients with recurrent priapism potentially eligible for randomized clinical trials of secondary prevention strategies.
Hypotheses:	Priapism is a common complication of sickle cell disease. In 5- to 10-year-old males with sickle cell anemia, it is hypothesized that the prevalence of priapism is 10%. In 10- to 15-year-old patients, it is hypothesized that the prevalence of priapism increases to 20%. In patients over 15 years old, it is hypothesized that the prevalence of priapism reaches 30%.
Primary Outcome:	Enumeration of the prevalence of priapism in males with sickle cell anemia and sickle beta zero thalassemia.
Secondary Outcome Measures:	
 1. Characterization of priapism in males with sickle cell anemia with reference to time of onset, duration of events, frequency of episodes, precipitating or associated activities, treatment modalities used, and outcome of treatments. 2. Descriptive comparison of the prevalence of priapism in males with sickle cell anemia to that described in older patients with other sickle hemoglobinopathies. 3. Assessment of general patient and parent understanding of priapism as a complication of sickle cell disease gained from completion of protocol. 4. Enumeration of patients available for clinical trials of secondary prevention.
Study Design:	Standardized questionnaire survey of 1,400 male patients with sickle cell anemia and 250 additional patients with any other form of sickle hemoglobinopathy receiving care in any Comprehensive Sickle Cell Center.
Study Population:	Males with sickle cell anemia and sickle beta zero thalassemia 5 years of age or older. Males with sickle beta plus thalassemia and sickle hemoglobin C disease 15 years of age and over.
Sample Size:	1,650 total; Each Center will be asked to survey a minimum number of male patients during a 7-month period, based on their patient population.
Human Subjects:	Level of risk low. Patients may feel uncomfortable discussing priapism with their medical provider. The training manual will include suggestions for how to aide patients in feeling comfortable with this discussion. However, the educational benefit of learning about this complication of their hemoglobinopathy should outweigh the risk. Patients are free to not answer any question if they are too uncomfortable and to withdraw from the study without penalty at any time.

4 ABBREVIATIONS

CSCC	Comprehensive Sickle Cell Centers
CRF	Case Report Form
EDC	Electronic Data Capture
DSMB	Data Safety Monitoring Board
GCP	Good Clinical Practice
ICH	International Conference on Harmonisation
HbSβ^0	Sickle Beta Zero Thalassemia
HbSβ^+	Sickle Beta Plus Thalassemia
HbSC	Sickle Cell Hemoglobin C Disease
HbSS	Sickle Cell Anemia
HIPAA	Health Insurance Portability & Accountability Act
IRB	Institutional Review Board
NHLBI	National Heart, Lung, and Blood Institute
PRC	Protocol Review Committee
SDMC	Statistics and Data Management Center, located at Rho Federal Systems Division, Chapel Hill, NC
US	United States

5 BACKGROUND AND RATIONALE

Priapism is an unwanted painful erection of the penis. It becomes more common with increasing age and vascular disease in the general population, and has been recognized as a complication of sickle cell disease since 1934. It occurs in two general patterns: (1) prolonged - an episode lasting 4 hours or more that carries with it a risk of permanent vascular damage and eventual impotence, and (2) stuttering - brief episodes that resolve spontaneously, often occur in clusters, but may herald a prolonged event.[1]

It is not known how many patients with sickle cell disease have experienced priapism. Historically, 5 to 10% of male sickle cell patients of any age were said to have had priapism.[2-5] Yet studies of adults with sickle cell disease now suggest that at least 30 to 45% of patients have a history of this complication.[6, 7] In a Jamaican survey of 104 patients with sickle cell anemia (HbSS), 42% (or 44 patients) had experienced at least one episode of priapism. The mean age at onset was 21 years, and no patient reported an episode before age 5 years.[7] Nigerian investigators, however, reported that 16% of male patients with sickle cell anemia and priapism were younger than 5 years of age.[8] A large review of published cases concluded that about half of all reported sickle cell patients with priapism had their first episode before they were 18 years old.[9] The systematic survey of male patients 5 to 20 years of age with sickle cell anemia reported from Dallas confirmed that the problem is common, with a cross-sectional prevalence of 27.5% and an actuarial incidence of $89\% \pm 9\%$ by 20 years of age.[1] Thus, priapism is a common problem even in children.

There is also a wide variation in frequency of episodes (one time only to daily for months or years, with 2 to 50% of patients reporting recurrent episodes), age at onset (toddler to adult), associations that promote the occurrence or ending of episodes, and eventual outcome (spontaneous resolution or impotence).[1] Retrospective surveys indicate that priapism is most common in patients with sickle cell anemia (HbSS), who account for 80 to 90% of reported cases.[5, 6, 9, 10] However it may occur in persons with all forms of sickle cell disease, and has even been reported to be increased in individuals with sickle cell trait.[9] A single episode of priapism was reported by 31 to 64% of patients, a pattern that appears to be more common in childhood.[1, 5, 7] About half of all patients, however, have recurrent episodes from 2 to 50 times per year.[6] The pattern of recurrent episodes is also very individual. Stuttering spells may occur every few days for months before stopping abruptly or heralding a prolonged episode.[7] Other investigators noted no clustering and related patients with years of unpredictable recurrent events.

The occurrence of priapism has been associated with higher levels of hemoglobin S[11] and found to be inversely correlated with levels of fetal hemoglobin[12] in specific populations. This is also suggested by the 42% incidence of priapism reported in Jamaican patients[7] compared to 2% of patients from Saudi Arabia where, on average, fetal hemoglobin levels are higher in HbSS patients.[13] Other investigators have observed no relationship to fetal hemoglobin levels.[5] Priapism has been suggested by some authorities to be more common in patients experiencing a severe course[5] of their

sickle cell disease and by others to not be associated with overall severity.[6] In the Dallas survey, no significant difference was found in the baseline hematologic values or number of hospital admissions for painful events between patients with and without a history of priapism.[1]

In the literature, 77% of priapism episodes reported occurred during sleep, 17% were related to sexual activity, and 3% each were related to excessive alcohol intake or were called spontaneous.[9] Today, cocaine or other drug use would probably be a more significant factor, at least in older adolescent and adult patients. In the Dallas survey, half of the patients reported that urination or use of oral opioid analgesics terminated episodes, while about one-third mentioned that mild exercise or bathing in warm water was effective. Further, one-third of the boys described the pain of priapism as the worst complication of their sickle cell disease.[1] None of these associations or therapies have either been prospectively investigated or validated in a large clinical cohort from the United States. Priapism remains the most common complication of sickle cell disease not investigated by the Cooperative Study of Sickle Cell Disease or the Comprehensive Sickle Cell Center Clinical Trials Consortium, until now.

This protocol will investigate the epidemiology of priapism by a survey of males over 5 years of age with all forms of sickle cell disease. This questionnaire is patterned after the published Dallas survey. Patients will be asked about the frequency, time of onset, and precipitating causes of priapism as well as the type of interventions that they have utilized to terminate episodes. These data will be correlated with age, hemoglobinopathy, baseline hematologic values, current therapy if any (i.e., hydroxyurea or chronic transfusion), prior history of prolonged episodes requiring aspiration and irrigation or shunt procedures for priapism, other complications of their sickle cell disease (chest syndrome, avascular necrosis, history of obstructive sleep apnea and/or prior tonsillectomy or adenoidectomy, hospitalization for painful events, stroke, and subarachnoid hemorrhage), and center location. Data from this survey will provide important information on the characteristics and frequency of priapism that will be of use in the design of future intervention strategies. In addition, the questionnaire will aid in the initiation of discussion about priapism between patients and clinical staff as well as making patients aware of the subsequent clinical intervention trials should they then or subsequently become eligible.

This clinical trial will be conducted in compliance with the protocol, International Conference on Harmonization (ICH), Good Clinical Practice (GCP) guidelines, and other applicable regulatory requirements.

6 STUDY OBJECTIVES AND PURPOSE

Primary Hypothesis:

Priapism is a common complication of sickle cell disease. In 5- to 10-year-old patients, it is hypothesized that the prevalence of priapism is 10%. In 10- to 15-year-old patients, it is hypothesized that the prevalence of priapism increases to 20%. In patients over 15 years old, it is hypothesized that the prevalence of priapism reaches 30%.

Objectives:

1. Enumerate the cross-sectional prevalence, demographics, and common clinical characteristics of priapism in males with sickle cell disease among the CSCC patient population.
2. Identify patients eligible for randomized clinical trials of promising secondary prevention strategies.

Specific Aim(s):

1. To conduct a questionnaire survey of 1,400 males with sickle cell anemia (HbSS) and sickle beta zero thalassemia (HbS β^0) 5 years of age and older in order to determine the prevalence (frequency) and characteristics (number and pattern of episodes, cause or precipitating event, treatment, and outcome) of priapism.
2. To survey 250 additional males with other forms of sickle cell disease with the same instrument and describe the occurrence and characteristics of priapism experienced.
3. To develop a structured educational brochure about priapism for patients with sickle cell disease.
4. To identify the number of patients with recurrent priapism potentially eligible for randomized clinical trials of secondary prevention strategies.

7 STUDY DESIGN

7.1 Treatment Plan

1. A one-page, culturally-sensitive, face-to-face interview will be conducted by trained center staff to ascertain patients' awareness of priapism as a complication of sickle cell disease. Prior to administering the questionnaire to patients less than 15 years of age, an explicit discussion will be held with his parent(s) or guardian(s) regarding the sexual content of the survey. The words and phrases used to question their child will be reviewed at this point, and the parent/guardian signature on the pediatric consent form will document that the discussion occurred.
2. If the patient or parent indicates that priapism has occurred, approximately 18 additional questions will be asked in order to characterize the episode(s).
3. The principal investigator at each local site will review all of the questionnaires from subjects who report that they have had an episode of priapism and indicate they have done so by initialing each questionnaire. If there are health issues identified that could require treatment or referral, the physician or clinic medical staff will discuss options for care with the participant and/or make appropriate referrals. Such issues include drug use, harmful sexual behaviors, or impotence. Subjects who report that they have never had an episode of priapism do not complete the entire questionnaire, and do not answer questions regarding any issues that could require referral.
4. A brief demographic Case Report Form will be completed for all participants who have signed the consent forms, regardless of their experience with priapism.
5. An educational brochure containing information about priapism, including available clinical trials, and a check for participating will be given to the patient or parent/guardian at the conclusion of the interview.

7.1.1 Primary and Secondary Endpoints

Primary Outcome:

Enumeration of the prevalence of priapism in males with sickle cell anemia and sickle beta zero thalassemia.

Secondary Outcome Measures:

1. Characterization of priapism in males with sickle cell anemia with reference to time of onset, duration of events, frequency of episodes, precipitating or associated activities, treatment modalities used, and outcome of treatments.
2. Descriptive comparison of the prevalence of priapism in males with sickle cell anemia to that described in older patients with other sickle hemoglobinopathies.
3. Assessment of general patient and parent understanding of priapism as a complication of sickle cell disease gained from completion of protocol.
4. Enumeration of patients available for clinical trials of secondary prevention.

7.2 Rationale for Study Design

The estimates of the frequency of priapism in men and boys with sickle cell disease vary widely. The definitions of priapism used, age and location of the population surveyed, as well as the training and sensitivity of the interviewer clearly may influence reports. This is the first large-scale survey of males of all ages with sickle cell disease in well-organized sickle cell programs. As such, it should escape the obvious biases of prior surveys of men seeking urologic consultation for impotence, studies of patients with the same disease but in different cultural settings (i.e., the African surveys), or studies involving pediatric patients only. It is a vital first step in determining the magnitude of the problem for patients with sickle cell disease. A rational intervention trial for this complication cannot be designed without the information from this study, numbers of patients, frequency of episodes, and treatments received.

A randomly selected subset of all US males with sickle cell disease would provide an ideal study population to determine the most unbiased estimate of the prevalence of priapism. Clearly, privacy and logistical issues eliminate this as a realistic choice of study design. Such a list does not exist and HIPAA concerns prohibit this approach. A more probable design would be to identify a random subset of all males known to participating Centers from a patient list or census. Unfortunately, few Centers are able to maintain a database such as this, and those that do report that patient contact information is often inaccurate, outdated, or incomplete. More importantly, confidentiality and privacy regulations prohibit the use of patient information for such purposes.

For these reasons, adult and pediatric male patients presenting to a Comprehensive Sickle Cell Center for follow-up, scheduled laboratory or transfusion, emergency department visit, or hospitalization will serve as the target population. Prevalence estimates obtained in this manner may be subject to ascertainment bias, limiting generalizability of the findings. However, these are the patients who are seen in clinical centers and for that reason they are a truer representation of the patients that knowledgeable clinicians typically see. There is no current literature to suggest whether or not males who experience other sickle cell-related complications or events are more or less likely to experience priapism, making prediction of the extent and direction of this bias impossible

to assess. Further, lack of an acceptable, affordable alternative study design supports the use of this approach. All publications from this study will identify the study population in detail and acknowledge the possibility of this potential bias.

By utilizing the significant clinical resources of the CSCC Clinical Trials Consortium and the established research infrastructure of the CSCC SDMC, this study can be conducted in a standardized and efficient fashion. Centralized training should help interviewers of both sexes to increase their comfort level with questioning and educating patients about priapism. While it may be beneficial to have male, African-American interviewers, this may not be possible in every center. Participating sites will be encouraged to carefully consider such factors in deciding whom to select to be trained to administer the questionnaire in their center. Role-playing and information in cultural contexts of this complication, possible only during a centralized training session, will enhance this study, future research efforts about priapism in sickle cell disease, and the clinical care of patients. Centralized data collection will be conducted via a web-based form that mirrors the CRFs (included in Appendices 1-3), a format that all clinical centers should be comfortable with from prior CSCC studies.

The educational pamphlet about priapism developed for this survey will provide a benefit to patients and their families in consolidating their knowledge about sickle cell disease and priapism. Copies of the pamphlet will also be available to educate patients who decline to participate in the study but who may be eligible for later intervention trials. This study is a vital first step in the rational approach to the design of intervention studies in priapism.

8 ELIGIBILITY AND DISCONTINUATION OF SUBJECTS

All males over age 5 with access to care in a Comprehensive Sickle Cell Center (CSCC) or participating institution associated with a CSCC (for interval follow-up, scheduled laboratory or transfusion, emergency department visit, or hospitalization) will be eligible for recruitment without regard to known history of priapism. The interview will be administered face-to-face by trained staff at each CSCC site who are knowledgeable about and comfortable discussing priapism. A professional who understands the cultural aspects of this and similar sensitive health behavior subject matter will train the interview personnel to use culturally recognizable and appropriate language during the interviews. Written materials from that presentation will become part of the training manual for the study. If the patient is experiencing a stressful clinical event such as painful crisis, consent may be obtained for the interview to be conducted in the future. Clinical staff will record the responses on the interview form during the interview. Participation from all 10 CSCCs is desirable. Centers may have more than one designated study site; therefore, as many as 20 clinical sites from the nine participating Centers may serve as sources for study enrollment. It is hoped that expedited Institutional Review Board (IRB) review and use of a brief written consent form will be acceptable to local IRBs for participation in this survey.

8.1 Inclusion Criteria

Subjects who meet all of the following criteria are eligible for enrollment into the study:

1. Subject or parent/guardian gives written informed consent.
2. Male with or sickle cell anemia or sickle beta zero thalassemia 5 years of age or over
- **OR** -
Male with sickle beta plus thalassemia or sickle hemoglobin C disease 15 years of age or over.
3. Subject and/or parent/guardian able to communicate adequately with the interviewer.

Subjects currently taking hydroxyurea, undergoing chronic transfusion, or participating in other research trials including those involving agents such as arginine are eligible for the study if all other entry criteria are met.

8.2 Exclusion Criteria

Subjects who meet any of the following criteria are disqualified from enrollment in the study:

1. Patient or parent/guardian declines participation.
2. Female.
3. Subject or parent/guardian unable to communicate adequately with the interviewer.

8.3 Subject Discontinuation

Subjects may decide to discontinue participation at any time during the interview. Investigators may discontinue any subject at their discretion if, in their professional opinion, the subject's health, safety, and/or well-being is threatened by continued participation in the study. The following circumstances may require discontinuation of subjects:

1. Patient or parent/guardian becomes emotionally distressed by questions or discussion.
2. Patient or parent/guardian requests discontinuation of the study.

Adverse events caused by participation in the study may necessitate modifications to the level of participation of a subject or discontinuation of a subject from the study. Subjects who discontinue early from the study before a full questionnaire is completed or for whom demographics cannot be obtained will be replaced by recruitment of additional subjects up to a maximum of 1,650 subjects.

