The 250 HbSC and HbS β^+ questionnaires will be from persons 15 years of age and older and in any proportion of those diagnoses. Each center will be encouraged to enroll all patients that they have available up to 25% of the total number of respondents in each age range until the total desired is reached. When a center enters 25% of the total patients in one age stratum, or the grand total of participants for an age stratum is reached, no further

questionnaires will be accepted by the SDMC from that center in that age stratum. Centers will be encouraged to continue to enter patients in other age strata.

We will estimate the priapism prevalence and its 95% two-sided confidence interval for 4 age groups: 5 to 9.9 years, 10 to 14.9 years, 15 to 24.9 years, and 25 years and older. To estimate the necessary sample sizes for each age group, we used the formula:

$$n = \frac{(2 \cdot 1.96)^2 (p)(1-p)}{(w)^2}$$

where w is the total confidence interval width, and p is the expected prevalence.

If an age group has a priapism prevalence of 15%, then 196 completed interviews are needed for a 0.10 wide 95% two-sided confidence interval for the estimated proportion of patients with priapism among patients with sickle cell disease. A group that has a priapism prevalence of 30% will need 323 completed interviews; 385 completed questionnaires are needed for a group that has a priapism prevalence of 50%. We would like to conduct more interviews in each category than these predictions suggest to be sure of obtaining adequate data to achieve the aims of this study. Specifically, we seek to obtain 1,400 complete interviews with accompanying demographic data according to the age distribution noted earlier. With the planned sample size and anticipated observed proportion of patients with priapism in each age range, each of the 4 two-sided 95% confidence intervals should have a total width of 0.10. The specified sample sizes for the 15 to 24.9 years strata and 25 or older may not be reached, in such a case the two-sided 95% confidence interval will have a total width larger than 0.10.

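### Replacing subjects who stop mid-interview can take known priapism-positive answers out of the primary prevalence, which may then be too low by an amount the protocol does not allow one to fix

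*Protocol*

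**What the plan says.** Section 7.1 describes a two-stage interview. Everyone receives a short first part. If the patient or parent reports that priapism has happened, about 18 more questions follow. The others stop early: "Subjects who report that they have never had an episode of priapism do not complete the entire questionnaire", and they are not asked about matters that might need referral, such as drug use, harmful sexual behavior or impotence.

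Section 8.3 lets a subject stop at any point: "Subjects may decide to discontinue participation at any time during the interview". One listed circumstance is "Patient or parent/guardian becomes emotionally distressed by questions or discussion". The replacement rule follows: "Subjects who discontinue early from the study before a full questionnaire is completed or for whom demographics cannot be obtained will be replaced", and this is done "by recruitment of additional subjects up to a maximum of 1,650 subjects".

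Section 10.1 expresses the primary sample in the same terms: "we seek to obtain 1,400 complete interviews with accompanying demographic data", divided by age stratum. Section 10.2 estimates prevalence in each stratum as an unadjusted proportion with a normal-approximation 95% interval. No section says what becomes of the answer of a subject who has reported priapism and then stops.

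**The concern.** The primary outcome is a proportion, and it is known as soon as the occurrence question is answered. A subject who answers no has, on the protocol's description, little or nothing of the interview left to abandon. A subject who answers yes still faces the long and sensitive part. If completing that part is the condition for being counted, the chance of being counted depends on the outcome being measured.

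A man who says yes and then stops would leave both numerator and denominator. At the hypothesized prevalences of 10% to 30% his replacement is more likely than not to be negative. The resulting error has one direction, is not reflected in the confidence interval and does not shrink with a larger sample.

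**Working it through.** **1. The plan's own figures.** Section 10.1 uses n = (2 × 1.96)² p(1 − p) / w² with w = 0.10. This gives 195.9, 322.7 and 384.2 for p = 15%, 30% and 50%. Rounded up, these are the stated 196, 323 and 385. The precision planning is correct, so the question is only who enters the proportion.

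**2. Does replacement imply removal?** The planned total is 1,400 + 250 = 1,650, and 8.3 caps recruitment with replacements at the same 1,650. If a replaced subject kept his place, there would be no room for his replacement under that cap once the targets were filled. With the complete-interview target in 10.1, the natural reading is that he does not count. This is an inference.

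**3. Size.** Let p be the true prevalence and d the share of positives who report priapism, then break off and are replaced, with no status-related loss among negatives. The expected estimate is

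p(1 − d) / [p(1 − d) + (1 − p)].

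The protocol gives no value for d, so 2% to 20% is an assumed range. At p = 30% and d = 10% the estimate is 0.27 / (0.27 + 0.70) = 27.8%. At d = 20% it is 0.24 / (0.24 + 0.70) = 25.5%. The prevalences of 10%, 20% and 30% are the hypotheses in section 6, 50% is the highest planning value in 10.1, and the stratum sizes are from 10.1. The half-width is 1.96 × √[p(1 − p)/n].

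| True p | n | Half-width (points) | Bias at d = 2% | d = 5% | d = 10% | d = 20% |
|---|---|---|---|---|---|---|
| 10% | 200 | 4.2 | -0.2 | -0.5 | -0.9 | -1.8 |
| 20% | 400 | 3.9 | -0.3 | -0.8 | -1.6 | -3.3 |
| 30% | 400 | 4.5 | -0.4 | -1.1 | -2.2 | -4.5 |
| 50% | 400 | 4.9 | -0.5 | -1.3 | -2.6 | -5.6 |

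At p = 30% and n = 400, coverage of the nominal 95% interval (normal approximation) is about 95%, 92%, 84% and 46% at the four values of d. The bias reaches the full half-width at d of about 44%, 23%, 20% and 18% for p = 10%, 20%, 30% and 50%.

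**4. Losses not tied to status.** With losses d1 among positives and d0 among negatives, the estimate is p(1 − d1) / [p(1 − d1) + (1 − p)(1 − d0)]. At p = 30%:

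- d1 = d0 = 10%: 0.27 / (0.27 + 0.63) = 30.0%, no bias.
- d1 = 10%, d0 = 2%: 0.27 / (0.27 + 0.686) = 28.2%, a bias of -1.8 points.
- d1 = 5%, d0 = 10%: 0.285 / (0.285 + 0.63) = 31.1%, so the direction reverses.

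Stopping before the status question, or missing demographics, therefore does no harm if equally frequent in both groups. Nothing in the protocol suggests that negatives are lost more often.

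**5. If recorded status is kept,** break-off after the answer has no effect on the expected estimate, whatever d is.

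**The case against.** The strongest reply is that 8.3 is an accrual rule. It says that further subjects are recruited; it does not say that answers already recorded are discarded. Section 10.2 names no complete-questionnaire analysis set, 7.1 asks for a demographic form from every consented participant, and 9.1 and 9.2 have forms completed for each subject and entered. A statistical analysis plan, not shown here, might keep such subjects. This stands in part: removal is inferred. But the protocol decides who counts toward the sample and makes no exception for known status.

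Second, the Human Subjects entry of the synopsis lets patients leave any question unanswered, separately from withdrawing, and 9.1 provides for explaining missing information. A man who reports priapism and declines the details need not be a discontinuation. This also stands, provided that such an interview counts as complete. The protocol does not define a full questionnaire. Read literally against 7.1, negative subjects never complete the entire one, so the term needs a definition by status in any case.

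Third, several features favor completion: a short single-visit interview, interviewer training, review of the wording with parents of patients under 15, deferral during a painful crisis, and payment at the end. They make low break-off plausible but do not establish it.

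Two stronger readings are tempting. One is that the primary prevalence is biased downward as a matter of fact. That needs both removal from the analysis and an appreciable break-off rate, and the protocol states neither. The other is that replaced subjects are mainly positive. That is not shown either, because losses before the status question and missing demographics can fall on anyone. At p = 10% with d1 = 10% and d0 = 2%, only 0.010 / (0.010 + 0.018) = 36% of those lost are positive, although a bias of -0.7 points remains.

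No existing safeguard covers the gap. The bias acknowledged in 7.2 comes from recruiting clinic attenders, and 10.1 tracks refusals, not break-offs after a positive answer.

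**Conclusion.** The concern holds as a possible downward bias of unknown size in the only primary outcome. Among subjects whose status is already known, those who break off the interview are priapism-positive, and the replacement rule together with the complete-interview target implies that they are not counted. The effect is negligible at about 2% break-off (half a point or less), modest at 5%, and material at 10% to 20% in strata with prevalence near 30%. It is smaller at 10% to 20% prevalence.

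The conclusion rests on three assumptions: that replaced subjects leave the prevalence sample, that breaking off is not handled as item non-response within a complete interview, and that other losses are about equal by status. Severity is moderate. The reason to act is that the direction is predictable and the cure is cheap, not that serious damage has been shown.

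**What to change.** In 8.3 and 10.1:

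- Base the primary prevalence on every consented HbSS/HbSβ⁰ subject with known age and genotype who answered the priapism-occurrence question, whether or not later questions were completed, to the extent that consent allows recorded answers to be kept after a subject stops.
- Replace only subjects who lack that answer, age or genotype.
- Define a complete questionnaire separately for subjects with and without reported priapism, and say whether skipped items count as complete.
- Use completed questionnaires for secondary outcome 1 (episode characteristics).
- Report break-offs by priapism status: positive, negative, or not yet known.

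The main cost is wording. Under section 8 and 9.1 answers are written on the paper form during the interview, so no new data are needed. The downside is some missing items in the episode-characteristics tables. The consent terms on keeping answers after a subject stops must be checked; those pages are not in the material reviewed, so it cannot be confirmed that wording is the whole cost.
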